14.1. Adverse events

An adverse event (AE) is defined as any untoward medical occurrence in a subject or clinical investigation subject administered a pharmaceutical product and which does not necessarily have a causal relationship with this

treatment. An AE can therefore be any unfavorable and unintended sign (including an abnormal laboratory finding), symptom, or disease temporally associated with the use of a medicinal (investigational) product, whether related to the medicinal (investigational) product, or not. Any event or laboratory abnormality that leads to a medical intervention, including withdrawal of IMP or significant additional concomitant therapy, will be considered an AE. Worsening of visual acuity determined by the Investigator to be due to progression of LHON will not be considered an AE.

AEs should be volunteered by the subject, be observed from examination of the subject at a clinic visit or be from observations of clinically significant laboratory values or other/special examination abnormal values. AEs will not be solicited by use of a specific list of anticipated events.

AEs will be coded to the SOC and PT using MedDRA central coding dictionary, Version 21.1 or higher.

Treatment-emergent adverse events (TEAEs) are defined as AEs that started on or after study treatment administration at Visit 3 or that represent an exacerbation of a condition that is present at baseline after treatment administration. See Appendix 2 for handling of partial dates for AEs. In the case where it is not possible to define an AE as treatment emergent or not, the AE will be classified by the worst case; i.e. treatment emergent.

Local (i.e. ocular) and systemic (i.e. non-ocular) AEs will be summarized separately. Ocular TEAEs will be summarized by treatment group for the first affected eye and second-affected/not-yet-affected eye separately. Systemic TEAE data will be summarized for the 2 treatment groups combined.

The following summaries will be produced for systemic AEs and ocular AEs separately using counts and percentages, i.e. number of subjects and percentage of subjects.

- Overall summary of AEs for the entire study, including the number of events reported
- TEAEs, including the number of events reported
- TEAEs by relationship to study treatment ('Unrelated', 'Unlikely', 'Related')
- TEAEs by relationship to study procedure ('Unrelated', 'Unlikely', 'Related')
- TEAEs by severity
- TEAEs leading to study discontinuation
- Serious TEAEs
- TEAEs leading to death, life threatening, hospitalization and other
- TEAEs of Special Interest (AESI)
- TEAEs of Special Interest (AESI) with IOP
- TEAEs of Special Interest (AESI) with intra inflammation

The following summaries will be produced for systemic AEs and ocular AEs separately using counts and percentages, i.e. number of subjects and percentage of subjects.

- TEAEs
- TEAEs related to study medication
- TEAEs related to study procedure

- Severe TEAEs
- TEAEs leading to study discontinuation
- Serious TEAEs
- TEAEs leading to death, life threatening, hospitalization and other
- TEAEs of Special Interest (AESI)
- TEAEs of Special Interest (AESI) with IOP
- TEAEs of Special Interest (AESI) with intra inflammation

Subjects are only counted once within each SOC or PT. Subjects with multiple events within a particular SOC or PT will be counted under the category of their closest drug-related event or procedure-related event within that SOC or PT for the summary tables by closest relationship to study drug and study procedure, respectively.

Subjects with multiple events within a particular SOC or PT will be counted under the category of their most severe event within that SOC or PT for the summary table of TEAE by maximum severity.

Within each systemic AE frequency table, the SOC's will be ordered in alphabetical order, and the PTs will be listed in descending order of frequency.

Within each ocular AE frequency table, the SOC's will be ordered in alphabetical order, and the PTs will be listed in descending order of frequency in the second-affected/not-yet-affected eye of the GS010 treatment group.

A summary of AEs leading to discontinuation will be provided, grouped by system organ class and preferred term.

A summary of SAEs will be provided, grouped by system organ class and preferred term.

A summary of AE leading to death will be provided, grouped by system organ class and preferred term.

In addition, a summary of AEs of intraocular inflammation and the concomitant medications administered for such events will be summarized, including the time course of the events and the concomitant medications.

All AEs recorded on the eCRF will be listed.

14.1.1. All TEAEs

Incidence of TEAEs related to study medication, TEAEs related to study procedure, and severe TEAEs will be presented by SOC and PT. A further tabulation presenting the PTs in descending order of frequency will also be presented.

Severity

Severity will be classified as mild/ moderate/ severe (increasing severity). TEAEs starting after the first dose of study medication with a missing severity will be classified as severe.

Relationship to Study Medication and to Study Procedure

Relationship, as indicated by the Investigator, will be classified as 'Unrelated', 'Unlikely', 'Possible' or 'Probable' (increasing severity of relationship), where:

- **Unrelated:** There is evidence of relationship to a cause other than the IMP/study procedures. Does not meet criteria listed under unlikely, possible or probable.
- **Unlikely:** Does not follow a reasonable temporal sequence from administration. Is most likely produced by the subject's clinical state or by environmental factors or other therapies administered.
- **Possible:** Follows a reasonable temporal sequence from administration. Is not likely produced by the subject's clinical state or by environmental factors or other therapies administered.
- **Probable:** Follows a reasonable temporal sequence from administration. Clear-cut temporal association with IMP.

A “related” TEAE is defined as a TEAE with a relationship to study medication and/or study procedure of ‘Possible’ or ‘Probable’. TEAEs starting after the first dose of study medication with a missing relationship to study medication and/or study procedure will be assigned a relationship of ‘Probable’.

14.1.2. Adverse events leading to discontinuation from study

TEAEs leading to discontinuation from study are those events recorded as “Withdrawal from study” on the AE page of the eCRF.

A summary of TEAEs leading to discontinuation from study by SOC and PT will be prepared. A listing of all AEs leading to discontinuation from study (non-TEAEs and TEAEs) will be provided.

14.1.3. Serious adverse events

Serious adverse events (SAEs) are those events recorded as “Serious” on the AE page of the eCRF.

A summary of serious TEAEs by SOC and PT will be prepared. A listing of all SAEs (non-TEAEs and TEAEs) will be provided.

14.1.4. Adverse events leading to death

TEAEs leading to death are those events which are recorded as “Fatal” on the Adverse Events page of the eCRF.

A summary of TEAEs leading to death by SOC and PT will be prepared. A listing of all AEs leading to death (non-TEAEs and TEAEs) will be provided.

14.1.5. Adverse events of special interest

The following AEs have been identified as AESI:

- Intraocular inflammation AE defined as any TEAE of the following MedDRA terms (all terms are PTs unless noted as an LLT):
 - Anterior chamber inflammation (anterior chamber cell, anterior chamber fibrin, anterior chamber flare, anterior chamber inflammation, anterior uveitis, aqueous fibrin, cyclitis, hypopyon, iridocyclitis, iritis, keratic precipitates)
 - Intermediate inflammation (autoimmune uveitis, pars planitis (LLT), vitreal cells, vitritis, vitreous haze, intermediate uveitis, intermediate inflammation, intermediate uveitis (LLT))
 - Posterior inflammation (choroiditis, chorioretinitis, retinitis, posterior inflammation)

- Non-specified eye inflammation (eye inflammation, uveitis)
- IOP increase

Note that the above terms are based on MedDRA version 21.1 and will be reevaluated and updated based on the most recent MedDRA version available.

In addition, a summary of AEs of intraocular inflammation and the concomitant medications administered for such events will be summarized, including the time course of the events and the concomitant medications.

For intraocular inflammation AE, duration of inflammation and maximal grade of inflammation will be described.

Likewise, a summary of AEs of IOP increase and the concomitant medications administered for such events will be summarized, including the time course of the events and the concomitant medications.

For IOP increase AE, duration of IOP increase will be described.

A patient listing of all ocular AEs will be provided.

14.1.6. Treatment for AEs related to elevation of IOP

Treatment of AEs with elevation of IOP will be described with number of patients using IOP lowering treatment (None/IOP agent lowering local alone/IOP agent lowering systemic alone/ local and systemic in association) for the first 6 months of follow-up and for the follow-up between 6 months and 1 year and for each year of follow-up after the first year.

Duration of treatment will be described.

14.1.7. Treatment for AEs related to intraocular inflammation

Treatment of AEs related to an intraocular inflammation will be described with number of patients using corticoids (None/local CS alone/systemic CS alone/ local and systemic in association) for the first 6 months of follow-up and for the follow-up between 6 months and 1 year and for each year of follow-up after the first year. Number and percent of inflamed eyes with at least 7 days of CS treatment will be described for each type of CS (local CS alone/systemic CS alone/ local and systemic in association) for the first 6 months of follow-up and for the follow-up between 6 months and 1 year and for each year of follow-up after the first year.

14.2. Deaths

If any subjects died during the study, as recorded on the “deaths” page of the eCRF, the information will be presented in a summary table and a by subject data listing.

14.3. Laboratory evaluations

The laboratory assessments that will be included in the reporting are:

- Hematology/serum chemistry
- Liver function tests
- Humoral immune response to AAV2
- Cellular immune response to AAV2

- Biodissemination

Quantitative laboratory measurements reported as “< X”, i.e. below the lower limit of quantification (BLQ), or “> X”, i.e. above the upper limit of quantification (ULQ), will be converted to X for the purpose of quantitative summaries, but will be presented as recorded, i.e. as “< X” or “> X” in the listings.

If the values are equal to “BLQ”, “BLD” or “<10” then impute them to 0.

Parameters will be assessed using descriptive statistics.

Hematology tests: Complete blood count including red blood cells, hemoglobin, hematocrit, white blood cells with differential and platelets.

Serum chemistry tests: Glucose, lipase, amylase, calcium, sodium, potassium, chloride, bicarbonate, blood urea nitrogen (BUN), creatinine and albumin.

Liver function tests: aspartate aminotransferase (AST), alanine aminotransferase (ALT), ALP, Gamma Glutamyl transferase (GGT) and total bilirubin.

For these three classes of laboratory tests, number of subjects with clinically significant abnormal values at each time point for each laboratory test will be described. A By-Subject Listing of all values + change for the parameter will be done for patients with at least one clinically significant abnormal value for the parameter. Number of subjects with available data (n), mean, SD, median, Q1, Q3, minimum and maximum at each time point for the absolute laboratory value by treatment groups will also be described.

For Liver function tests only, an additional analysis will be done: for each parameter, the number of patients above 2x(upper limit of normal range of the parameter) and the number of patients above 3x(upper limit of normal range of the parameter) will be described by timepoints and by groups.

Humoral and Cellular Immune Responses Against Recombinant Adeno-Associated Virus 2 (rAAV2) and biodissemination

For each visit: Number patients with positive and negative values will be performed. Positivity will be defined with laboratory.

Only for positive rAAV2 (>0 for Cellular Immune Responses -don't included '<10'- and ≥0 for Humoral Immune Responses): the number of subjects with available data (n), mean, SD, median, Q1, Q3, minimum and maximum at each time point for the absolute laboratory value by groups will be described and a graph of mean value overtime will be provided on a logarithmic scale.

Quantitative laboratory measurements will be compared with the relevant laboratory reference ranges in SI units and categorized as:

- Low: Below the lower limit of the laboratory reference range.
- Normal: Within the laboratory reference range (upper and lower limit included).
- High: Above the upper limit of the laboratory reference range.

14.4. ECG evaluations

The results will be determined to be normal, abnormal but not clinically significant or abnormal clinically significant by the Investigator for screening and for comparison to post-treatment assessments.

The number and percentage of subjects with normal, abnormal but not clinically significant and abnormal clinically significant ECG findings will be summarized by visit. Additionally, shift tables showing changes between baseline and EOS (2 years) will also be produced.

All ECG data will be listed by subject.

14.5. Vital signs

The following vital signs measurements will be reported for this study:

- Seated Systolic Blood Pressure (mmHg)
- Seated Diastolic Blood Pressure (mmHg)
- Seated Pulse Rate (bpm)
- Temperature (°C)

Systolic and diastolic blood pressures, temperature, and pulse rate will be displayed in summary tables including number of subjects with available data (n), mean, SD, median, Q1, Q3, minimum and maximum at each visit. The descriptive statistics for change from baseline will be presented in the same way.

Individual data listings of systolic and diastolic blood pressure, temperature, and pulse rate will be produced for all subjects over time. The data will appear in ascending order by subject ID, parameter, and date of measurement in this listing.

14.6. Physical examination

Physical examination will include general appearance, skin, head, eyes, ears, nose, throat, neck, thyroid, chest/lungs, heart, abdomen, lymph nodes, extremities, height and body weight.

Physical examination results from the visit will be categorized as normal or abnormal and shifts from baseline to the most abnormal post-baseline assessment will be summarized by body system.

14.7. Other safety assessments

14.7.1. Goldmann Applanation Tonometry

Intra ocular pressure (IOP) measurements in mmHg (including post-injection IOP measurements on the day of injection) will be summarized at all timepoints (included 30 min post injection measure) using summary statistics for continuous variables, by treatment groups for the treated eye and comparative eye separately.

For post-injection measurements and for IOP measured during an ocular inflammation AEs, following statistics will be provided by treatment groups for the treated eye and comparative eye separately:

- Distribution of duration of ocular inflammation AEs,
- Number and percentages of elevated IOP. An elevated IOP is defined as a value of IOP > 22 mmHg,
- Distribution of mean IOP during ocular inflammation AEs
- Distribution of maximum IOP during ocular inflammation AEs,

- Duration that IOP > 22 mmHg (days) defined as date of last value > 22 mmHg – date of first value > 22 mmHg, (if only one value time=1 day)

For eyes with at least one elevated IOP, a listing of all values of IOP for these eyes will be provided. Following information will be provided in the listing: study name, subject number, treatment arm, eye concerned, date of injection, date of examination, time between examination and injection and IOP value.

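### SAP 14.7.1 takes duration of IOP > 22 mmHg as last minus first elevated date, so it includes time between separate elevations and can score two same-day elevations as 0 days

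*SAP*

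**What the plan says.** SAP 14.7.1 sets the threshold: "An elevated IOP is defined as a value of IOP > 22 mmHg". It then lists statistics "For post-injection measurements and for IOP measured during an ocular inflammation AEs", one of which is the duration of elevation. The start, end and exception are given as "Duration that IOP > 22 mmHg (days) defined as date of last value > 22 mmHg" minus "date of first value > 22 mmHg, (if only one value time=1 day". The section does not end an elevation at a reading of 22 mmHg or below, and it has no rule for several elevated readings on one date.

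Readings on the injection day enter the general IOP summaries, among them one taken 30 minutes after injection. The duration statistic is to be shown "by treatment groups for the treated eye and comparative eye separately". SAP 14.1 uses a different split for ocular events: "Ocular TEAEs will be summarized by treatment group for the first affected eye and second-affected/not-yet-affected eye separately".

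Neither document gives another formula. SAP 14.1.5 makes IOP increase an event of special interest and says its duration will be described, without saying how.

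**The concern.** Protocol 6.2.5 treats raised IOP as an expected potential effect of the injection and says the LHON optic nerve may be more vulnerable to it, whether transient or sustained. Duration is the statistic that should separate those two patterns. A last-minus-first rule can blur them in both directions. Two brief spikes far apart look like one long elevation, and an eye with two elevated readings on one day can score lower than an eye with one.

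The split by eye adds a second difficulty. In the bilateral arm both eyes receive GS010, so a treated/comparative division has no clear meaning there, and SAP 14.7.1 does not define the terms.

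**Working it through.** **Inputs.** The rule and its exception come from SAP 14.7.1. Visit days come from Protocol 9.2 and SAP 5.3 (Days 1, 14, 28, 56, 84, 168, 252, 365, 548 and later), with IOP measured at each. The schedule's tonometry footnote refers to more than one post-dilation time point at the treatment visit, and SAP 5.4 admits unscheduled visits, so several readings on one date are possible. Which readings are above 22 mmHg is assumed for illustration.

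**Formulas.**
- SAP rule: last elevated date − first elevated date; 1 day if there is one elevated value.
- Unbroken runs: for each run of consecutive readings > 22 mmHg, last elevated date − first elevated date + 1, summed over runs.

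The only figure in the rule is the 1 day for a single value. It reproduces, but only through the exception, because plain subtraction gives 0.

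| Elevated | Normal in between | SAP rule (days) | Unbroken runs (days) |
|---|---|---|---|
| Day 0, one reading | – | 1 (exception) | 1 |
| Day 0, two readings | – | 0 − 0 = 0 | 0 − 0 + 1 = 1 |
| Days 0 and 1 | – | 1 − 0 = 1 | 1 − 0 + 1 = 2 |
| Days 14 and 28 | no reading | 28 − 14 = 14 | 28 − 14 + 1 = 15 |
| Days 0 and 28 | Days 1, 14 | 28 − 0 = 28 | 1 + 1 = 2 |
| Days 1 and 84 | Days 14, 28, 56 | 84 − 1 = 83 | 1 + 1 = 2 |
| Days 84 and 365 | Days 168, 252 | 365 − 84 = 281 | 1 + 1 = 2 |

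The first three rows show the loss of monotonicity: 1, 0, 1. The last three show calendar time being counted across normal readings. Adding 1 to the SAP rule would repair the first problem only; Days 1 and 84 would still score 84.

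**Dependence on scope.** If the phrase about post-injection measurements means injection-day readings, spans there are short and the same-day zero is the main defect. If it means every reading after injection, spans can reach years. For readings within an inflammation adverse event, the span is limited by the event. Even so, Protocol 14 does not report intermittent events as multiple events, so one record may cover quiet intervals.

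**An alternative that does not work as the main measure.** Suppose an episode ended at the first later reading ≤ 22 mmHg, counted as end − start + 1. If the next scheduled visit is normal:
- Days 84 and 365: (168 − 84 + 1) + (548 − 365 + 1) = 85 + 184 = 269 days, against 281.
- Days 0 and 28: (1 − 0 + 1) + (56 − 28 + 1) = 2 + 29 = 31 days, against 28.

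On so sparse a schedule, that rule mainly counts the gaps between visits. It can serve as an upper bound, not as the duration itself.

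**The case against.** The best defence has four parts.

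- **Any rule is a convention.** IOP between visits is unobserved, so no formula recovers true duration. This stands, and is why the result should be labelled as observed minimum duration. It does not justify counting time across readings that were observed to be normal.
- **The large figures need a scope that the SAP does not state.** This stands. The 281 days arise only if all later visits are in scope or one inflammation event spans Days 84 to 365. Neither scope reading removes both defects.
- **The same-day zero is a wording gap.** The exception "if only one value time=1 day" suggests that a 1-day minimum was intended. If it means one date, two same-day readings score 1. The text does not say so, and the number of injection-day readings is set in an injection guide that is not in the documents, so how often this would occur is unknown.
- **The safety question is covered elsewhere.** SAP 14.1.5 and 14.1.6 describe IOP adverse events, their time course and their treatment. SAP 14.7.1 summarises IOP at all time points and lists every value for any eye with an elevation. This limits the harm, but the duration table itself could still mislead.

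A reader might infer that normal readings are being classed as elevated. They are not: the count and percentage of elevated readings use each reading's own value. A reader might also infer a bias towards one arm or a threat to the efficacy result. The documents support neither. SAP 14 excludes safety comparisons between arms unless specified, none is specified for IOP, and nothing fixes the direction of any error.

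**Conclusion.** The point holds in a limited form. Read literally, the rule includes calendar time between separate elevations even when the readings between them are normal, and it is not monotone in the number of elevated readings. The size runs from a 1-day anomaly (0 against 1) on an injection day to 281 days against 2 in the Day 84 and Day 365 example. The larger figure rests on the scope assumption and on illustrative readings; the zero rests on taking one value to mean one reading.

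The consequence is confined to a descriptive summary for an event of special interest. The primary endpoint, all tests, the counts of elevated readings and the full listing are unaffected. The correction is worth making because it is cheap and the statistic is meant to tell transient from sustained elevation.

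**What to change.** In SAP 14.7.1:

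1. Define an episode as an unbroken run of readings > 22 mmHg in the same eye, with duration = last elevated date − first elevated date + 1. One or more elevated readings on a single date count as 1 day, and no date is counted twice in the total.
2. Report the number of episodes, total days and longest episode per eye.
3. Label the result as observed (minimum) duration. The date of the next reading ≤ 22 mmHg may be shown as an upper bound, left open where no later reading exists.
4. State whether the post-injection readings in scope are those of the injection day or all later ones.
5. Present the table by arm for first-affected and second-affected/not-yet-affected eyes, as SAP 14.1 does for ocular events.

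The cost is one changed derivation in the safety programs and a relabelled table. No new data are needed.
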